5.2 Analysis Plan (see Detailed Statistical Analysis Plan Attached)

All patients will be included in the analysis based on their randomization assignment at time of enrollment. The unit analysis will be completed at the participant-level. We will conduct descriptive statistics to evaluate balance between demographic (i.e., sex, age, race/ethnicity) and clinical variables (i.e., stage of cancer, diagnosis of cancer) between both the randomized and control groups. To assess our primary outcome of the effect of the intervention on acute care use within 6-months post-enrollment we will assess % of patients with acute care use. We will create a (composite measure for acute care use that includes both ED visits and hospitalizations. To compare risk of acute care use (composite measure) and individual ED and hospital use within 6 months post-enrollment, we will use Cox regression models. We will also compare counts of total ED visits and hospitalization (composite measure of acute care use) within the first 6 months, using General Estimating Equation with Poisson family, log link, and independent correlation.

For secondary outcomes of ED and hospital use within 12 months, we will compare use using GEE models. We will compare counts of total ED visits and hospitalization (composite measure of acute care use) within 12 months, using General Estimating Equation (Poisson) with an offset term for length of follow-up. To compare goals of care discussion and documentation, Advance Directive

documentation, Physician Order for Life Sustaining Treatment documentation, Chemotherapy, Radiation, Surgery, hospice, and palliative care within 12 months, we will use GEE models to compare odds of documentation or use across groups. For end-of-life health care use, we, we will compare any ED use and hospital use prior to death (30 days prior) and proportion of participants with palliative care and hospice use using the models described above among participants who died during the 12-month study.

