Interim analyses every 6 months will evaluate point estimates and trends to inform refinements to the protocol. Descriptive statistics and exploratory data analyses will be conducted as needed to evaluate protocol process measures with key outcomes identified.

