5.3 Sample Size

The goal is to reduce acute care use. Based on data from St. Jude Hospital, the mean number of acute care visits per member per year is 1.45. Local site oncologist in the pre-review assessment anticipated at least a 55% difference in risk of acute care use among participants in the intervention group as compared to the control group. For this trial, we estimated that a sample size of 128 participants would have at least 90% power with a 2-sided type I error rate of 0.05 to detect at least a

55% difference in risk of acute care use in the intervention group compared with the control group based on effect sizes from our ongoing VA pilot and other pilot studies. For this trial, we expect to obtain point estimates with an understanding that we may not reach significance in this study.

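### Do the six-monthly interim reviews need a written limit on what they may change?

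*Combined protocol and SAP*

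**What the plan says.** Section 5.2 ends with two sentences on interim work. The first is "Interim analyses every 6 months will evaluate point estimates and trends to inform refinements to the protocol". The second is "Descriptive statistics and exploratory data analyses will be conducted as needed to evaluate protocol process measures with key outcomes identified". Neither says whether summaries are pooled or split by arm, who sees them, or which parts of the protocol may be refined. The heading of 5.2 adds "see Detailed Statistical Analysis Plan Attached", but the combined document has no separate text of that kind.

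For the 6-month question, 5.2 lists three kinds of analysis:
- a percentage: "our primary outcome of the effect of the intervention on acute care use within 6-months post-enrollment we will assess % of patients";
- Cox models: "To compare risk of acute care use (composite measure) and individual ED and hospital use within 6 months post-enrollment";
- a Poisson GEE: "We will also compare counts of total ED visits and hospitalization (composite measure of acute care use) within the first 6 months".

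None of the three is named as primary. Section 5.1 is wider still: under the primary outcome it also lists hospice and palliative referrals, coach contacts and symptom changes.

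Section 5.3 claims "at least 90% power with a 2-sided type I error rate of 0.05", and then says "we expect to obtain point estimates with an understanding that we may not reach significance in this study". Section 6.4 requires IRB approval before any protocol change takes effect. Appendix A titles the study a pilot test.

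**The concern.** Repeated interim estimates that feed into protocol changes are a known way to lose control of a trial. If the team sees results by arm, and nothing is declared fixed, it could move to the outcome or model that looks best so far and then test it at an unadjusted 0.05. The final p-value would be too small and the estimate too favourable. The plan also leaves something to choose between, because 5.2 does not rank its 6-month analyses and 5.1 lists several measures. IRB approval is a route for making changes; it does not limit what interim results may change. Since the trial claims 90% power at two-sided 0.05, readers will treat it as a test.

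**Working it through.** **1. The plan's own figure: is it a fixed design?** The inputs are 64 per arm, 1.45 visits per member per year and a 55% difference (5.2 and 5.3). The 6-month control risk is not given. Assuming a constant Poisson rate, it is 1 − exp(−1.45/2) = 0.516. A 55% relative reduction gives 0.45 × 0.516 = 0.232.

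- Mean risk 0.374; SE under the null = √(2 × 0.374 × 0.626/64) = 0.0855.
- SE under the alternative = √((0.516 × 0.484 + 0.232 × 0.768)/64) = 0.0818.
- Power = Φ[(0.284 − 1.96 × 0.0855)/0.0818] = 92%.

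This fits the stated 90% or more, with one final comparison at 0.05 and no allowance for interim tests.

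**2. Looks alone.** If significance were tested at 1.96 at each of 2, 3 or 4 equally spaced looks (counting the last), two-sided error would be 8.4%, 10.8% or 12.6%. The plan describes no such test and no stopping rule, so these figures do not apply. If no version of coaching has an effect, changing how coaching is delivered cannot create a difference between arms. Section 5.2 analyses all patients as randomised, so a later refinement cannot drop anyone already enrolled. One fixed final test stays at 5.0% two-sided, or 2.5% in the intervention's favour.

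**3. Steering by arm.** Assume three outcomes (composite, ED, hospital) with equal correlation r and no true effect. At information fraction t, the outcome with the lowest z is chosen and then tested on all data, with final z = √t × interim z + √(1 − t) × increment. The results below come from 2,000,000 simulated trials.

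| r | Favourable tail, t = 0.25 | t = 0.5 | t = 0.75 | No look, best of three at the end | Two-sided, t = 0.5 |
|---|---|---|---|---|---|
| 0.4 | 4.60% | 5.48% | 6.12% | 6.60% | 5.91% |
| 0.6 | 4.20% | 4.93% | 5.47% | 5.93% | 5.63% |
| 0.8 | 3.67% | 4.19% | 4.58% | 4.92% | 5.31% |

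In every row the steered look lies below the no-look column. This must be so: whichever outcome the look picks is one of the three, and its final z cannot be lower than the lowest of them. The look therefore adds nothing to what an unranked list already allows.

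**4. The choice that 5.2 actually leaves open.** Percentage, Cox and count analyses of the same composite would be more closely correlated than three different outcomes. With r assumed at 0.9–0.95, half-information steering gives 3.3–3.7% in the favourable tail and 5.1–5.2% two-sided.

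**5. How far a mid-trial estimate could guide anyone.** With 32 per arm followed for 6 months and 51.6% having an event, there are 64 × 0.516 = 33.0 events. SE(log HR) = √(4/33.0) = 0.348, so the 95% interval spans a factor of exp(1.96 × 0.348) = 1.98 either side. If the hazard ratio were 0.45, expected events would be 16.5 and 8.9, the SE √(1/16.5 + 1/8.9) = 0.416, and the interval 0.20 to 1.02. This makes by-arm estimates a poor guide to refinement, but imprecision is not an error in the plan.

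**6. Reading the sentence in context.** The second interim sentence concerns process measures. Section 4.0 has the supervising nurse see that the protocol is followed and deal with problems in the coach's workflow, and 5.1 collects the timing, length and frequency of coach contacts. Refining coaching delivery is the natural meaning, and step 2 shows that it is harmless to the test.

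**The case for a change.** The best case for a change is that it would be cheap. A few sentences could base refinements on pooled and process data, fix the primary outcome and analysis, and still allow descriptive summaries by arm. The second interim sentence mentions key outcomes as well as process measures, so it does not exclude by-arm effects. Section 4.0 makes the Protocol Director responsible both for amendments and for overseeing analysis, and nothing in the document separates the two. Selection would also bias the estimate, which is what 5.3 says the study expects to deliver.

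The silence is real, and one clarifying line would do no harm. But the case needs by-arm steering that no section plans, and it assumes that the cited detailed SAP is silent too. A rule on interim reviews would also leave the main source of exposure in place unless a primary analysis were named. Naming one is a different decision with its own consequences. On the control risk above, a Cox model has Φ(√(50.8/4) × |ln 0.45| − 1.96) = 81% power if 55% means a hazard ratio of 0.45. If 55% means a relative risk reduction, HR = ln(1 − 0.232)/ln(1 − 0.516) = 0.36, and with 47.9 events power is 94%. That choice, and the wider outcome list in 5.1, should not be settled through a sentence on interim reviews.

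**Conclusion.** The gap is one of missing detail, which analysts would fill sensibly, and following the plan as written produces no wrong result. Looks and coaching changes cost nothing in type I error. In the assumed worst use of a half-information look, two-sided error is 5.3–5.9% against 5.0%, with 4.2–5.5% in the favourable tail against 2.5%. An end-of-trial choice with no look exceeds this, at 4.9–6.6% in the same tail.

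These figures rest on assumed correlations and on an assumed information fraction, since section 3.3 gives no enrolment duration. They describe multiplicity from unranked 6-month analyses, not a fault of the interim reviews. With a pilot that openly expects estimates rather than significance, IRB approval of every change, and a cited SAP that may already hold the rule, no amendment to the interim sentence is needed.

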5.3 Sample Size

The goal is to reduce acute care use. Based on data from St. Jude Hospital, the mean number of acute care visits per member per year is 1.45. Local site oncologist in the pre-review assessment anticipated at least a 55% difference in risk of acute care use among participants in the intervention group as compared to the control group. For this trial, we estimated that a sample size of 128 participants would have at least 90% power with a 2-sided type I error rate of 0.05 to detect at least a

55% difference in risk of acute care use in the intervention group compared with the control group based on effect sizes from our ongoing VA pilot and other pilot studies. For this trial, we expect to obtain point estimates with an understanding that we may not reach significance in this study.

6.0 DATA MANAGEMENT CONSIDERATIONS

6.1 Data Management

The Protocol Director and participating site investigators will maintain adequate and accurate participant case histories with observations and other data pertinent to the study. Original source documents will be transcribed to data collection tools and used to communicate study data to the lead site.

Participating site PI will be responsible for maintaining the clinical protocol and subjects' study charts, reporting adverse events, assuring that written, informed consent is obtained and documented, and reporting the status of the trial in continuing renewals submitted to their IRB and trial monitoring group(s) as per their facility protocol.

6.3 Confidentiality

Members of the local team will be responsible for database records of patient data. The data will be kept in the central online database, under password protection with access limited to specific areas of the database. A chart with all of the relevant research patient information will be maintained for each patient at each institution by the local team for that specific institution. Stanford PI and Study Coordinator may review patient charts for yearly audits.

APPENDIX A: PARTICIPANT ELIGIBILITY CHECKLIST

A Participant Eligibility Checklist is completed and signed by an Investigator prior to obtaining signed informed consent. The eligibility checklist is filed in the subject's research chart.

Existing medical information in the patient's medical record will be used as supporting documentation of eligibility.

Protocol Title:	Pilot Test Health Care Coach Program
Protocol Number:	35626
Principal Investigator:	[name] MD MPH

II. Subject Information: Subject Name/ID: Gender: Male Female

III. Study Information:

SRC Approved IRB Approved Contract signed

IV. Inclusion/Exclusion Criteria

	Inclusion Criteria	Yes	No	Supporting Documentation*
	(From IRB approved protocol)			
1.	Patient has been newly diagnosed with cancer, except non-melanoma skin cancer, non-metatastic thyroid cancer, and prostate cancer not requiring Medical Oncology as described above in the protocol with stages of disease as outlined in protocol.			
2.	Patient is age 18 or older			
3.	Patient will receive all future care at local site			
4.	Ability to consent			
	Exclusion Criteria (From IRB approved protocol)			
1.	Inability to consent			
2.	Cancer diagnosis does not require Medical Oncology			
3.	Patient is pregnant			

	Patient is already receiving home care or palliative care					
	5. Patient is younger than 18 years					
	Patient will not receive subsequent care at local site					
	*All subject files must include supporting do					
	confirmation can include, but is not limited report, and medical record review.	l to, laborat	ory test resu	ults, radiology test results, subjec	ct selt-	
	cporr, and medical record review.					
By signing This stuce finalized	ement of Eligibility Ing this form of this trial I verify that this subjectly is approved by the Stanford Cancer Institution If financial and contractual agreements as sement Group.	itute Scienti	fic Review (Committee, the Stanford IRB, a		
	Treating Physician Signature:		Date) :		
	Printed Name:					
	Secondary Reviewer Signature:			Date:		
	Printed Name:					
			1			
	Study Coordinator Signature:		Date	e:		
	Printed Name:					
•
